5.3.2.2. Previously untreated symptomatic CLL

In addition, two studies were conducted in previously untreated symptomatic CLL subjects (Chen, 2008), (Ferrajoli, 2008).

Chen treated previously untreated symptomatic CLL subjects with single agent lenalidomide. The starting dose for lenalidomide was initially 10 mg daily with weekly 5mg dose escalations to the target dose of 25 mg daily x 21 days every 28 day cycle. Toxic events in the first 2 subjects (TLS requiring dialysis; neutropenic sepsis) led to a study halt with DSMB review, and subsequent protocol amendments to reduce both the starting and target doses (2.5 mg and 10 mg, respectively, days 1-21), slow the dose escalation rate (2.5 mg cycle 1, 5 mg cycle 2, 10 mg cycle 3 and thereon), extend allopurinol TLS prophylaxis to a minimum of 3 cycles, and increase frequency of TLS lab monitoring. Deep vein thrombosis (DVT) prophylaxis with low dose aspirin was mandated. Steroids were allowed for management of TFR symptoms as needed. Twenty-five (25) subjects have been enrolled on the amended protocol. The median age is 60 (range 33-78), 10 subjects (40%) were Rai stage III-IV, bulky nodes were present in 9 subjects (36%), organomegaly in 23 pts (92%). Twenty-three (23) subjects have received at least 1 cycle and are evaluable for toxicity. Ten (10) subjects (43%) developed grade 3-4 neutropenia during at least 1 cycle (at doses 2.5-10 mg) which was the most common cause for dose reductions/interruptions. Six (6) subjects have required intermittent GCSF support (none requiring routine use). Three (3) subjects (13%) developed grade 3-4 thrombocytopenia (without bleeding). The most common non-hematologic toxicities were: Fatigue (74%), nondesquamating rash (48%), all were reported as grade 1-2. Infections (43%) were mostly minor non-neutropenic respiratory/sinus/skin infections. TFR occurred in 18 subjects (78%). Although most subjects experienced TFR in the first week on study, many also continued to experience flare symptoms with subsequent cycles (30.6% of all 186 cycles). Most tumor flare symptoms resolved spontaneously but eight subjects required steroids on at least one occasion with prompt resolution. Four (4) subjects were hospitalized for febrile neutropenia and/or pneumonia. No further TLS has been noted. Seventeen (17) subjects have completed at least 3 cycles and are evaluable for response. Eleven (11) subjects (65%) have achieved a PR, 6 SD (35%), and none have progressed. Responses were reached at a median of 4 cycles (range 2-15). Although dramatic lymphocyte reductions were seen as early as week 1 (lenalidomide dose 2.5 mg/d), rebound during cycle days 22-28 off-drug were common. Two subjects have withdrawn from the study due to lack of response after 10 cycles (SD) and prolonged Grade 3-4 neutropenia and thrombocytopenia, respectively. The median daily tolerated dose is 10 mg with 26% of subjects requiring dose reductions to 5 mg (most due to cytopenias).

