response/relapse < 6 mo), 42% had prior FCR or PCR and 21% had prior alemtuzumab. The TLS prevention strategy resulted in only 2 (3.8%) cases of TLS, both observed at 2.5 mg/daily (1 patient with Grade 2 and another with lab TLS). Grade 3/4 tumor flare occurred in 5 (9.6%) patients and was managed with NSAIDs or low-dose steroids. The most common Grade 3/4 adverse events (AEs) included neutropenia (65%) and thrombocytopenia (33%). Febrile neutropenia occurred in 4 (8%) patients. Grade 3/4 infections were observed in 21 (40%) patients; 10 (19%) patients developed pneumonia and 3 developed sepsis; 2 cases of sepsisrelated death at day 37 and 94 of therapy were also noted but deemed unrelated to study drug by the investigators. Reasons for study discontinuation included disease progression (37%), AE's (29%), consent withdrawal (15%), death (4%), other reasons (10%). For 16 (31%) patients, 2.5 mg/daily was the maximum dose reached and 22 (42%) patients were unable to escalate beyond 5 mg/daily. Grade 4 neutropenia was the primary reason for delay in dose escalation. By intentto-treat (ITT) analysis, 6 patients (12%) had a partial response (NCI-WG 1996), 30 patients (58%) had stable disease and 13 patients (25%) progressed; 3 patients were non-evaluable. Median duration of treatment was 3.1 months (range, 0.07-18.4) and the median time to response was 4.3 months (range, 2.8-7.4). Responses were observed at 10 mg/daily (n=3), at 15 mg/daily (n=1), and at 20 mg/daily (n=2); Median PFS (ITT) was 5.5 months and median PFS for responders was 12 months. Three patients still remain on therapy and were transferred to commercial lenalidomide. (Data on file at Celgene)

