Febrile Nautropopia	ANC < 1,000/μL with fever	Interrupt lenalidomide therapy
Neutropenia	(temperature ≥	 Follow CBC every 7 days
	38.5°C)	Use of growth factors (G-CSF, GM-CSF) is permitted at the investigator's discretion
		 Resume lenalidomide (decrease one dose level) when febrile neutropenia has resolved with ANC ≥ 500/μL
		Re- escalation to the next consecutive dose level is permitted as follows: Continue Conti
		 If subject restarts dosing at one dose level lower on Day 1 to Day 14 of a cycle, and completes the remainder of that cycle at this lower dose without occurrence of toxicities requiring dose interruption/reduction, then the subject may be dose re-escalated to next consecutive-dose level starting at Day 1 of the subsequent cycle.
2	- If subject restarts dosing at one dose level lower on Day 15 to Day 28 of a cycle, and completes the remainder of that cycle and the subsequent cycle at this lower dose without occurrence of toxicities requiring dose interruption/reduction, then the subject may be dose re-escalated to next consecutive-dose level starting at Day 1 of the following cycle.	
Thrombocytopenia	Platelets	Interrupt lenalidomide therapy
	$<$ 20,000/ μ L	 Follow CBC every 7 days
	- Resume lenalidomide (decrease one dose level) when platelet count recovers to \ge 25,000/μL	
	Re-escalation to the next consecutive dose level is permitted if the subject completes one full cycle without occurrence of toxicities requiring dose interruption/reduction.	

Table 5: Dose Reduction and Modification Guidelines for Lenalidomide (Continued)

Toxicity	Severity	Action	
Tumor Flare	Grade 3 or 4	 Interrupt lenalidomide therapy and initiate therapy with corticosteroids, NSAIDs and/or narcotics 	
		 Resume lenalidomide (decrease one dose level) when symptoms resolve to ≤ Grade 1 	
		 Re-escalation to the next consecutive dose level is permitted at Day 1 of the subsequent cycle when Tumor Flare resolves to ≤ Grade 1. 	
Desquamating (blistering) rash	Any	 Permanently discontinue lenalidomide and follow for PD 	
Non- desquamating rash	Grade 3	 Interrupt lenalidomide therapy. 	
uesquamating rasii		 Resume lenalidomide when the rash resolves to ≤ Grade 1 (decrease one dose level) 	
Non- desquamating rash	Grade 4	Permanently discontinue lenalidomide and follow for PD	
Neuropathy	Grade 3	Interrupt lenalidomide therapy.	
		 Resume lenalidomide when the neuropathy resolves to ≤ Grade 1 (decrease one dose level) 	

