Neuropathy	Grade 4	Permanently discontinue lenalidomide and follow for PD	
Venous thrombosis/emboli	≥ Grade 3	Hold (interrupt) dose and start anticoagulation;	
sm	4,	 Resume lenalidomide at investigator's discretion (maintain dose level). 	
Hyperthyroidism or hypothyroidism	Any	Interrupt lenalidomide and initiate appropriate medical therapy.	
		 Resume lenalidomide at investigator's discretion (maintain dose level). 	

Table 5: Dose Reduction and Modification Guidelines for Lenalidomide (Continued)

Toxicity	Severity	Action
Serum Creatinine	Grade 2	Interrupt lenalidomide
`	(> 1.5 - 3.0 x ULN)	Evaluate subject weekly (minimum) until the serum creatinine return to baseline
	OR	If serum creatinine resolves to < Grade 1 resume lenalidomide (decrease one dose level)
	Grade 3 (> 3.0 - 6.0 x ULN)	If serum creatinine has stabilized to grade 1 after a minimum of 3 weeks of dose interruption resume lenalidomide at the investigator's discretion (decrease one dose level)
		 If serum creatinine has not stabilized to ≤ grade 1 after 5 weeks of dose interruption:
		 Permanently discontinue lenalidomide and follow for PD at the investigator's discretion OR Contact the Celgene Medical Monitor to discuss subject status
		 If the serum creatinine worsens at any time to > Grade 3, or if dialysis is indicated, permanently discontinue lenalidomide and follow for PD
	pR(Upon resumption of lenalidomide, evaluate subject weekly x 2 weeks to ensure the serum creatinine does not worsen; if the serum creatinine again worsens during those 2 weeks, permanently discontinue and follow for PD
Serum Creatinine	Grade 4 (> 6.0 x	
Sorum Creatinine	ULN) OR	Permanently discontinue lenalidomide and follow for PD
	if dialysis is indicated	

Table 5: Dose Reduction and Modification Guidelines for Lenalidomide (Continued)

Toxicity	Severity	Action
TLS	Laboratory TLS or Grade 1 TLS	Same dose of lenalidomide will be continued without interruption or dose reduction at the investigator's discretion.
		 Hospitalize subjects with Grade 1 TLS, (hospitalization for laboratory TLS will be per investigator's discretion)
		 Provide with vigorous intravenous hydration and rasburicase therapy as needed to reduce hyperuricemia, until correction of electrolyte abnormalities.
		 Dose escalation to the next consecutive dose level is permitted when laboratory TLS is resolved and Grade 1 TLS is resolved to Grade 0.
TLS	≥ Grade 2	Interrupt lenalidomide therapy.

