		 Resume lenalidomide (at the next lower dose level) when the TLS resolves to Grade 0.
		 If lenalidomide is resumed prior to the start of the subsequent cycle, a chemistry test should be performed every other day for the first week following re-initiation of lenalidomide.
		 Re-escalation to the next consecutive dose level is permitted after completion of one full cycle without laboratory TLS or ≥ Grade 1 TLS, or occurrence of toxicities requiring dose interruption/reduction.

Table 5: Dose Reduction and Modification Guidelines for Lenalidomide (Continued)

Toxicity	Severity	Action
Liver Function Tests (LFTs) Liver Function	ALT > 3.0 and ≤ 5.0 x ULN and serum total bilirubin ≤ 1.5 x ULN ALT > 3.0 and ≤	Continue current dose level Test at next scheduled visit Interrupt levelidemide thereby
Tests (LFTs)	5.0 x ULN and a serum total bilirubin > 1.5 x ULN OR ALT > 5.0 x ULN OR Serum total bilirubin > 1.5 x ULN	 Interrupt lenalidomide therapy. Evaluate ALT and serum total bilirubin weekly until both return to baseline levels Resume lenalidomide when ALT and serum total bilirubin return to baseline. Maintain dose level if recovery from event occurs ≤ 14 days from initial test result. Decrease by one dose level if recovery from event is prolonged > 14 days but ≤ 28 days from initial test result. Continue to monitor weekly LFTs during this cycle. If the event does not repeat, dose escalation or reescalation may continue according to protocol. Medical monitor must be notified if values do not return to baseline within 28 days of the initial event.
Other lenalidomide- related non- hematologic AEs	≥ Grade 3	 Interrupt lenalidomide therapy. May resume lenalidomide when the adverse event resolves to ≤ Grade 2 (decrease one dose level or maintain dose level per the investigator's discretion)

Lenalidomide dose may be interrupted/modified per the investigator's discretion for any AE (any Grade) not outlined in Table 5.

Dose escalation or re-escalation may begin on the scheduled Day 1 of a new cycle according to the protocol guidelines if toxicities requiring dose interruption and/or modification have resolved as specified in Table 5.

If there is a dose interruption during a cycle that lasts beyond Day 28 of the cycle, the subject must still have assessments as per Table 2 every 28 days. An unscheduled visit may be conducted to meet this requirement.

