21.3. Cairo-Bishop Definition and Grading of Tumor Lysis Syndrome (Cairo, 2004)

Cairo-Bishop Definition of Laboratory Tumor Lysis Syndrome (LTLS)

Uric Acid	\geq 476 µmol/l (\geq 8.0 mg/dl) or 25% increase from baseline	
Potassium	\geq 6.0 mmol/l (\geq 6.0 mEq/l) or 25% increase from baseline	
Phosphorous	\geq 1.45 mmol/l (\geq 4.5 mg/dl) or 25 % increase from baseline	
Calcium	\leq 1.75 mmol/l (\leq 7.0 mg/dl) or 25% decrease from baseline	ON

Laboratory tumor lysis syndrome (LTLS) is defined as either a 25% change or level above or below normal, as defined above, for any two or more serum values of uric acid, potassium, phosphate, and calcium within 3 days before or 7 days after the initiation of chemotherapy. This assessment assumes that a patient has or will receive adequate hydration (\pm alkalinization) and a hypouricaemic agent(s).

Cairo-Bishop Definition of Clinical TLS

The presence of laboratory TLS and one or more of the following criteria:

- 1. Creatinine: ≥ 1.5 ULN (age ≥ 12 years or age adjusted)
- 2. Cardiac arrhythmia / sudden death
- 3. Seizure*

ULN, Upper limit of normal

Cairo-Bishop Grading System for TLS

Grade	LTLS	Creatinine	Cardiac Arrythmia	Seizure
0	-	≤1.5 x ULN	None	None
1	+	1.5 x ULN	Intervention not indicated	None
2	+	> 1.5 – 3.0 x ULN	Non-urgent medical intervention indicated	One brief generalized seizure; seizure(s) well controlled or infrequent; focal motor seizures not interfering with ADL
3	ţC)	> 3.0 – 6.0 x ULN	Symptomatic and incompletely controlled medically or controlled with device	Seizure in which consciousness is altered; poorly controlled seizure disorder; breakthrough generalized seizures despite medical intervention
4	+	> 6.0 x ULN	Life-Threatening	Seizures of any kind that are prolonged, repetitive, or difficult to control
5	+	Death*	Death*	Death*

LTLS, laboratory tumor lysis syndrome; ULN, upper limit of normal; ADL, activities of daily living

^{*}Not directly attributable to a therapeutic agent

^{*}Probably or definitely attributable to clinical TLS

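### Table 5 tells sites both to restart and to stop for good after severe renal tumor lysis syndrome, and nothing says which row governs

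*Protocol*

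**What the plan says.** All the dosing rules at issue sit in Protocol Section 10.2.3, Table 5.

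- **TLS, Grade 2 or worse.** Drug is interrupted, and then: "Resume lenalidomide (at the next lower dose level) when the TLS resolves to Grade 0". Re-escalation is allowed after a full clean cycle. One action covers every grade from 2 upward.
- **Serum creatinine, Grade 2 or 3.** Drug is interrupted and may restart one level lower on recovery, with this limit: "If the serum creatinine worsens at any time to > Grade 3, or if dialysis is indicated, permanently discontinue lenalidomide and follow for PD".
- **Serum creatinine, Grade 4 (above 6.0 × ULN), or dialysis indicated.** "Permanently discontinue lenalidomide and follow for PD".

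TLS is graded by Appendix 21.3, which defines clinical TLS as "The presence of laboratory TLS and one or more of the following criteria"; raised creatinine is one of those criteria. Its grading table puts creatinine above 6.0 × ULN at Grade 4. Neither the TLS row nor the creatinine rows mention the other, and the creatinine rows make no exception for rises caused by TLS.

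**The concern.** Renal injury is one of the ways TLS becomes severe, so the two sets of rows will often describe the same patient. Over part of that overlap one row orders a restart and the other forbids it. A site that looks up the diagnosis, finds the TLS row and follows it as written would re-expose a subject whom the creatinine row takes off drug permanently.

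The event is not hypothetical for this drug. Section 5.3.2.2 reports TLS needing dialysis among the first two subjects of the untreated-CLL study. Section 5.3.2.3 reports two deaths among the subjects who developed TLS in the original CLL-001 design. Safety is the primary endpoint here, and adverse events leading to discontinuation are tabulated (Protocol Section 15.8, SAP Section 12.1). The row a site chose would therefore also decide how such a subject is counted.

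**Working it through.** No formula applies. The check sets the rows against the TLS grades and then looks for a rule of precedence.

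**Step 1: overlap of the rows**

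| Situation | TLS row (Grade 2 or worse) | Serum creatinine rows | Can both be followed? |
|---|---|---|---|
| (a) TLS with creatinine > 6.0 × ULN: TLS Grade 4 and creatinine Grade 4 | Interrupt; restart one level lower at TLS Grade 0 | Permanent stop | No |
| (b) TLS Grade 2 or 3 with dialysis indicated | Interrupt; restart one level lower at TLS Grade 0 | Permanent stop | No |
| (c) TLS Grade 2 or 3 by creatinine (> 1.5 to 6.0 × ULN), no dialysis | Interrupt; restart one level lower at TLS Grade 0 | Interrupt; restart one level lower on creatinine recovery | Yes, by waiting for the later criterion |

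The restart condition in (a) and (b) can be reached. TLS Grade 0 requires creatinine at or below 1.5 × ULN with no laboratory TLS, arrhythmia or seizure, and a subject can recover to that after a Grade 4 rise. The contradiction is confined to (a) and (b).

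**Step 2: is there a tie-breaker?**

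- The discretion clause after Table 5 covers "discretion for any AE (any Grade) not outlined in Table 5". Both toxicities are in the table, so it does not apply.
- The next clause lets escalation or re-escalation begin "if toxicities requiring dose interruption and/or modification have resolved as specified in Table 5". It does not govern the first restart.
- Contact with the medical monitor is triggered by a 5-week interruption. TLS may resolve sooner, and the clause ranks nothing.
- Section 10.5 allows an investigator to stop drug on judgment. It permits a stop but does not require one.
- Appendix 21.1 says that a laboratory abnormality forming part of a syndrome is recorded only as the syndrome. This is a recording rule, but it could steer a site to the TLS row.
- Reporting of serious events within 24 hours and the need to contact the sponsor for new drug make a wrong restart less likely. Neither says which row applies.

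**Step 3: how Table 5 treats other severe toxicities**

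Non-desquamating rash and neuropathy each have a separate Grade 4 row ordering a permanent stop. Grade 3 or 4 tumor flare may be restarted. Severity alone therefore does not tell the reader which action is meant for TLS.

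**Step 4: how often it could arise**

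- Amended CLL-001 (Section 5.3.2.3): 2 TLS cases in 52 subjects, described as "1 patient with Grade 2 and another with lab TLS". Above Grade 2: 2 − 1 − 1 = 0 of 52.
- The relapsed/refractory study starting at 10 mg reported no TLS; the study starting at 25 mg reported 5%, all Grade 3.
- Original CLL-001: four TLS cases in 18 subjects by Section 5.3.2.3 (an amendment summary counts five). No creatinine values or grades are given, so cases meeting (a) or (b) cannot be counted.

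These studies used other starting doses and schedules or report too little detail, so no projection to the 104 enrolled subjects is made.

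**The case against.** The strongest reply is that the rows can be reconciled. TLS can reach Grade 2 to 4 through arrhythmia or seizure without renal injury, so the TLS row has content of its own and the creatinine rows can be taken to carry the renal component. On that reading, resolution of TLS lifts only the TLS hold; the creatinine stop remains, and a site that restarted would breach an unqualified instruction printed immediately above the TLS rows. An amendment summary says detail was added on stopping drug permanently for renal insufficiency, which points to the same intent.

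This is a sensible reading and probably the intended one, but it is not written. A reader could as reasonably take the TLS row, being specific to the cause, as the governing one, and the amendment summary shows intent without ranking the rows.

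The points about frequency stand. The dialysis case arose with weekly escalation from 10 mg, whereas this trial escalates every 28 days; after that study lowered its doses and extended prophylaxis, no further TLS was seen. Entry here excludes creatinine clearance below 60 mL/min and previous renal failure requiring dialysis. Amendment 6 says that few subjects remain on drug, and none was randomized after 2012. Editing Table 5 now would protect very few people, and no document shows that any subject in this trial met both rows.

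**Conclusion.** The concern holds. For TLS with creatinine above 6.0 × ULN, or TLS of Grade 2 or worse with dialysis indicated, Table 5 gives two incompatible orders and the Protocol supplies no precedence. This is a contradiction in a safety rule, which goes beyond missing detail. The number affected is likely very small and cannot be estimated from the documents; prospective exposure under Amendment 6 is minimal. No efficacy endpoint, analysis population or censoring rule in the SAP is defined by this dosing rule. The case for correcting it rests on the seriousness of a wrong restart and the low cost of the correction. It assumes that the creatinine rows apply whatever the cause of the rise, which is how they are worded.

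**What to change.** Make two additions to Table 5 at the next amendment:

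1. In the row for TLS of Grade 2 or worse: *If creatinine is > 6.0 × ULN or dialysis is indicated, permanently discontinue per the Serum Creatinine row.*
2. Below the table: *If more than one row applies, the most restrictive action governs.* This also settles restart timing when creatinine is between 1.5 and 6.0 × ULN.

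If the sponsor does intend restart after such events, it should instead exclude TLS-related rises from the creatinine rows.

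For subjects already treated, check the TLS and creatinine records once for anyone who met both rows, and note the action taken when discontinuations due to adverse events are reported. The cost is two sentences and that one check; no new eCRF field is needed.

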10.3. Emergency Unblinding

This is now an open label protocol. Therefore the dose of study drug will be identified on the package labeling.

10.4. Prior/Concomitant Medications

All medications (prescription and non-prescription), treatments and therapies taken from 28 days prior to Cycle 1 Day 1 through the last dose of study drug, must be recorded on the eCRF.

10.4.1. Prophylaxis and/or Treatment for TLS, TFR, Neutropenia, and Thromboembolic Events

10.4.1.1. Tumor Lysis Syndrome (TLS) Prophylaxis

TLS prophylaxis, comprising of oral hydration and allopurinol 300 mg/day will be initiated at least 3 days prior to starting study drug and for a minimum of the first 3 treatment cycles. For subjects with known allergy to allopurinol prior to study initiation or for those who develop an allergy during the course of study, the medical monitor should be contacted. To maintain fluid intake, subjects must be instructed to drink 8 to 10 eight ounce (240 mL) glasses of water each day for the first 14 days of each cycle during the dose escalation period. Hydration levels should be adjusted according to age and clinical status, and lowered if the subject's cardiovascular status indicates the possibility of volume overload.

Subjects will be monitored for TLS as follows:

- On Day 2 and 4 and then weekly (Days 8, 15, 22) for cycle 1 and the first cycle of each dose escalation
- On Day 1, 8 and 15 of cycle 2 (if not dose escalated)
- At least every 28 days thereafter and as clinically indicated.

10.4.1.2. Tumor Flare Reaction (TFR) Treatment

Grade 1 TFR may be treated with NSAIDs and TFR \geq Grade 2 may be treated with corticosteroids. Narcotic analgesics may be added as needed for pain control in subjects experiencing \geq Grade 2 TFR.

Subjects will be monitored for TFR as follows:

- On Day 2 and 4 and then weekly (Days 8, 15, 22) for cycle 1 and the first cycle of each dose escalation
- On Day 1, 8 and 15 of Cycle 2
- At least every 28 days thereafter and as clinically indicated.

